A standard non-invasive blood pressure cuff (e.g., American Diagnostics Corporation, Hauppauge, NY but any one can be used off the shelf) and disposable plastic clamp (e.g., Medline Industries Incorporated, Mundelein, IL) can be used to apply RIC in patients resuscitated from OHCA via three cycles of 5-mins. inflation to 200 mmHg followed by 5-mins. deflation of a blood pressure cuff on a thigh. The cuff occludes the artery; the clamp maintains pressure in the air bladder of the cuff during the inflation periods. No additional benefit is associated with more than three inflations, or with treatment of more than one limb. Note that no device is approved by the Food and Drug Administration to provide RIC in the United States.

This ED-based study will identify human and other factors that may decrease the ability to implement the autoRIC device in patients with OHCA. The study will also confirm the safety of the device for use in the field. This study will use exception from informed consent for emergency research.

PRIMARY AIM FOR PILOT STUDY

Our primary aim is to evaluate the feasibility of random allocation to active RIC (intervention) versus (vs.) sham RIC (control) quickly upon ED arrival following resuscitation from OHCA. Feasibility will be assessed as attrition, defined as the proportion of randomized subjects who do not remain on allocated therapy for the intended study duration. In the intervention group, this will be defined as lack of completion of three cycles of inflation-deflation; In the control group, this will be defined as crossover to the intervention group. Included will be subjects with spontaneous circulation upon ED arrival after receiving chest compressions by emergency medical services (EMS) providers or defibrillation by laypersons or EMS providers. Excluded will be: ST elevation on first electrocardiogram; written do not attempt resuscitation; pregnant; prisoners; trauma, drowning, or hypothermia etiology of arrest; known dialysis fistula; or limb amputation. Enrolled will be 30 patients. All outcomes will be summarized descriptively. The design of a future trial will be modified based on the results of this study.

PRIMARY HYPOTHESIS FOR PILOT STUDY

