The null hypothesis is that the attrition rate will be not more than 25%. We assume 59 patients annually are treated by EMS providers for OHCA (21 due to ventricular fibrillation) and have spontaneous circulation upon arrival at the participating receiving hospital. Enrollment of 30 patients (15 per group) will allow estimation of attrition with precision (as measured by half-width of 95% CI) of at least 16.8% overall (and 23.7% within each group).

BACKGROUND AND SIGNIFICANCE

BURDEN

Out-of-hospital cardiac arrest (OHCA) is common, lethal and debilitating. Cardiac arrest has multiple etiologies,

and presumptions about the etiology of arrest influence treatment decisions. Sometimes an identifiable precipitating cause is evident (e.g. traumatic injury, drowning, strangulation, or overdose). In these cases, treatment is directed not only to restoration of circulation, but also to addressing the underlying medical conditions. The majority of OHCA without obvious physical cause is secondary to acute coronary occlusion. In all cases, treatment is directed toward timely restoration of blood flow to the heart and brain.

Extrapolation from observational data reported to the Resuscitation Outcomes Consortium (ROC), suggests that about 424,000 calls to 911 are made annually for individuals who are presumed to have had a non-traumatic OHCA in the United States.⁽⁴⁾ Many of these patients are in such serious condition upon EMS arrival that no attempts at resuscitation are made. Outcome is generally poor among all patients with OHCA treated by EMS; only about 55% of treated cardiac arrest patients having a perfusing rhythm upon transport to an ED, with only 10% of those treated surviving to discharge.

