Clinical research resources are limited. The effectiveness of interventions must be demonstrated definitively if claims of their health benefit are to have scientific credibility.⁽⁹⁵⁾ Since some experts endorse RIC,^(40, 96) while others question its merits,⁽⁹⁷⁾ we believe that a large trial of RIC after OHCA will inform future public policy. Planning a multi-center trial to evaluate the effectiveness of the intervention in this population is premature without preliminary evidence of its efficacy. The present study will assess the feasibility of applying the intervention early after restoration of circulation to justify the investment of limited resources in a large trial. To date, no trial has evaluated RIC in patients with cardiac arrest.

OTHER DESIGNS CONSIDERED

Note that RIC can be applied in the field or in the ED. But also note that electrocardiograms, defibrillators and fibrinolytic therapy were studied and used in the coronary care unit or ED before diffusing to the out-of-hospital setting. We believe that the feasibility of RIC needs to be demonstrated in the ED setting before this therapy diffuses to the out-of-hospital setting.

We previously conducted pilot studies that showed that IH by iced intravenous saline in patients resuscitated from OHCA was feasible either in hospital or in the field,^(1, 2) but the subsequent large trial showed that IH in the field was associated with an increased incidence of rearrest as well as pulmonary edema.⁽³⁾ Since implementation of RIC in the field may delay other important elements of care, and the benefit of RIC is unclear, we believe that demonstration of the feasibility of randomization in the emergency department (ED) setting is necessary before proceeding to an assessment of its effectiveness in the out-of-hospital setting.

PRELIMINARY EXPERIENCE WITH RIC IN PATIENTS WITH ACUTE CARDIOVASCULAR ILLNESS

We applied RIC to six patients resuscitated from OHCA or with presumed STEMI in our ED, using a manual cuff to inflate to 200 mmHg for five minutes then deflate for five minutes, clamp to reduce air leak during cuff inflation, and stopwatch to time each cycle. All patients underwent three cycles of cuff inflation-deflation. Two (33%) had air leak > 20 mmHg from the cuff, requiring manual reinflation during treatment. We have modified the use of the clamp to reduce air leak.

RESEARCH DESIGN AND METHODS

DESIGN

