All medical assistants who work in the ED of the participating hospital have been trained in how to apply RIC. These individuals completed a minimum of 720 clock hours of training in medical assisting skills to be certified as medical assistants by Washington State before the start of their employment in the ED. As such, their training most closely resembles that of entry level firefighter/emergency medical technicians. Each medical assistant will be required to demonstrate proficiency in application of the active and sham autoRIC device before study enrollment begins. Anyone who is not proficient will receive corrective training then be required to demonstrate proficiency.

Standard post-resuscitation care will be mandated and monitored as in the control group.

MONITORING OF CONCURRENT CARE

Initial critical care management of patients with EC has an influence on subsequent neurological recovery and survival.^(101, 103, 104, 118, 119) Case-control studies have evaluated the effectiveness of combinations of hospital-based treatments in patients resuscitated from cardiac arrest in a variety of settings.^(105-109, 120) All of these studies reported improved outcomes vs. historical controls. As well, greater survival to discharge was associated with greater adherence to recommended hospital-based post-resuscitative care guidelines.⁽¹²¹⁾ Collectively, these studies demonstrate that hospital-based care of patients with OHCA impacts outcomes and may modify the effect of interventions evaluated in a trial. Failure to monitor these elements of care may attenuate the effect of the study treatment.

A summary of use of mandated, monitored and prohibited care processes, without patient outcome, will be provided to hospital providers at least quarterly. If performance deviates from expectations, we will work with hospital providers to address these concerns.

STUDY ASSESSMENTS

Screening and Pretreatment Assessments

There is limited time for screening and pretreatment assessments in this trial because of the acute life-threatening nature of OHCA. Study personnel will screen each OHCA patient transported to the recruiting hospital. Information about patient baseline characteristics and processes of care will be abstracted from the clinical record after enrollment.

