The initial neurological⁽¹²²⁾ and cardiopulmonary status⁽¹²³⁾ upon hospital arrival are important determinants of outcomes after OHCA. Also, the initial degree of cardiopulmonary failure upon hospital arrival is predictive of subsequent development of multi-organ failure. Treating providers will be asked to document neurological status (assessed using the Full Outline of UnResponsiveness [FOUR] score)⁽¹²⁴⁾ and cardiopulmonary dysfunction (assessed using Serial Organ Failure [SOFA] score)⁽¹²⁵⁻¹²⁷⁾ before randomization. These scores are important covariates and will be useful for exploratory secondary analyses.

Documentation of Treatment

This will be assessed as treatment assigned; treatment received; time points used to monitor the time-dependent nature of the intervention including call to 911, sustained restoration of spontaneous circulation (ROSC), initiation of RIC, completion of treatment cycles.

Monitoring for Outcomes

Study staff will review subject's clinical record daily to monitor for outcomes and potential adverse events as well as to monitor use of concomitant treatments.

PRIMARY OUTCOME

Attrition assessed as the proportion of randomized subjects who do not remain on allocated therapy for the intended study duration among subjects randomly allocated. In the intervention group, this will be defined as lack of completion of three cycles of inflation-deflation; In the control group, this will be defined as crossover to the intervention group. Secondary and Exploratory Outcomes

Treatment Success assessed as the proportion of intervention group patients who remain alive and on their allocated therapy for the intended study duration.

Cardiac Function assessed as left ventricular ejection fraction (LVEF) using echocardiograms ordered for clinical indications.

Cardiogenic Shock assessed as systolic BP < 80 mmHg during any 6 h period within 48 h of the index arrest not due to a correctable cause, and treated with pressors or inotropes or placement of a mechanical cardiac assist device (e.g. intra-aortic balloon pump). Cardiogenic shock correlates with survival after resuscitation from cardiac arrest.^(21, 123)

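### Does a 25% attrition benchmark that names no arm hide poor delivery of RIC?

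*Protocol*

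**What the plan says.** The Primary Aim and Primary Outcome sections of the protocol define attrition as a single proportion among all randomized subjects, with an event that differs by arm. In the intervention group it is "lack of completion of three cycles of inflation-deflation; In the control group, this will be defined as crossover to the intervention group".

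The benchmark appears under Primary Hypothesis and again under Sample Size: "The null hypothesis is that the attrition rate will be not more than 25" per cent. Neither place names an arm. The Primary Hypothesis section adds that 30 patients, 15 per group, allow "estimation of attrition with precision (as measured by half-width of 95% CI) of at least 16.8% overall (and 23.7% within each group".

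The Analyses section says that all outcomes are summarized descriptively, without statistical comparison, and that no claims will be made from the results. On their use, the Primary Aim section says: "The design of a future trial will be modified based on the results of this study".

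Other provisions bear on the RIC arm alone:

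- Documentation of Treatment records assigned treatment, received treatment, the start of RIC and the completion of cycles.
- Treatment Success is a secondary outcome in intervention patients only.
- Device Failure, under Safety Outcomes, records early discontinuation for mechanical reasons.

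**The concern.** The two events differ in kind. A RIC patient counts as attrition unless staff finish three manual cycles during emergency care. A control patient counts only if someone actively delivers RIC. If crossover is uncommon, nearly all events come from the RIC arm while controls supply half of the denominator.

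The protocol also describes a purpose that concerns the RIC arm. The Rationale for Current Pilot Study says: "The present study will assess the feasibility of applying the intervention early after restoration of circulation". The opening rationale says: "This ED-based study will identify human and other factors that may decrease the ability to implement the autoRIC device". Neither statement has a benchmark of its own. Treatment Success has none either, and because it also requires survival it is not simply one minus RIC-arm attrition.

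The worry is that a pooled figure within 25% could be read as good feasibility and carried into a larger trial although a third or more of RIC patients did not complete treatment.

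**Working it through.** **Inputs.** 30 patients, 15 per group; benchmark 25%; stated half-widths 16.8% and 23.7% (Primary Hypothesis). Prior completion data are six patients (Preliminary Experience): "All patients underwent three cycles of cuff inflation-deflation". The protocol gives no crossover rate, so every crossover figure below is an assumption.

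**1. The plan's own precision.** Half-width = (upper limit − lower limit)/2 of the exact (Clopper-Pearson) 95% interval, at the first whole count above 25%:

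- 8/30: 12.28% to 45.89%, half-width 16.8%.
- 4/15: 7.79% to 55.10%, half-width 23.7%.

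Both stated figures are reproduced. This is not the only route. The simple normal formula 1.96 × √(p(1−p)/n) at p = 0.325 gives 1.96 × √(0.219375/30) = 16.8% and 1.96 × √(0.219375/15) = 23.7%. The figures therefore do not prove that the planners had 25% in mind within each arm. They do show that an estimate within each group was planned. (Sample Size attaches the same two figures to accrual instead of attrition. That is a separate wording matter and does not affect this point.)

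**2. What a pooled 25% allows.** 0.25 × 30 = 7.5, so the largest count is 7 (7/30 = 23.3%; 8/30 = 26.7%). Maximum RIC non-completers = 7 − crossovers:

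| Control crossovers | Maximum RIC non-completion | Exact 95% CI |
|---|---|---|
| 0 | 7/15 = 46.7% | 21.3% to 73.4% |
| 1 | 6/15 = 40.0% | 16.3% to 67.7% |
| 2 | 5/15 = 33.3% | 11.8% to 61.6% |
| 3 | 4/15 = 26.7% | 7.8% to 55.1% |
| 4 | 3/15 = 20.0% | 4.3% to 48.1% |

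Within the RIC arm alone, 0.25 × 15 = 3.75, so at most 3/15 lies within 25%. From four crossovers on, the two readings no longer conflict in this direction.

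**3. How often the readings would part.** Take X ~ Bin(15, p) in the RIC arm and Y ~ Bin(15, c) in controls. P(X + Y ≤ 7 and X ≥ 4) is:

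| True RIC non-completion p | c = 0% | c = 5% | c = 10% | c = 20% |
|---|---|---|---|---|
| 20% | 35% | 33% | 29% | 17% |
| 30% | 65% | 58% | 47% | 25% |
| 40% | 70% | 56% | 42% | 20% |

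The first row is not evidence of masking. At a true 20%, delivery is within 25%, and an observed 4/15 or more is sampling noise. P(X ≥ 4) there is 0.352, of which 0.348 coincides with a pooled rate within 25% when there is no crossover. Only the rows for 30% and 40% describe poor delivery. Six of six completions would occur with probability 0.7^6 = 0.118 at 30% and 0.6^6 = 0.047 at 40%. These data do not exclude such rates, but they do not point to them.

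**4. Would anyone be misled?** Suppose the result is 7/15 and 0/15. The primary outcome reads 7/30 = 23.3%. The arm-specific definition, the planned within-group precision and the recorded cycle completion all yield 7/15 = 46.7%. Treatment Success could be at most 8/15, since non-completers fail it and any deaths can only lower it. No rule turns 23.3% into a decision to proceed.

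**5. What a separate 25% reading in the RIC arm would add.** At n = 15 the observed rate would exceed 25% in 6%, 18% or 35% of trials at true non-completion of 10%, 15% or 20%. It could serve only as a loose descriptive reference.

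**The case for a change.** The strongest case for the concern is that the protocol states the 25% itself, twice, and never says what it applies to. A later analysis plan would therefore have an unclear target to work from. It is also the only yardstick for the primary outcome of a study meant to shape the next trial, and one or two sentences would settle it without new data.

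Part of this stands. The benchmark sentence names no denominator, the pooled reading is inferred from the single-proportion definition, and the six earlier patients (exact two-sided upper limit for non-completion 45.9%) cannot rule out 30% or 40%.

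The rest does not. Terms such as met or passed presuppose a pass/fail use of 25% that the protocol does not contain. The primary aim is whether patients can be randomized quickly on arrival and kept on their allocation, and crossover by controls is a failure of that aim just as non-completion is. Crossover is a real possibility: "All medical assistants who work in the ED of the participating hospital have been trained in how to apply RIC". The statements about applying the intervention and finding obstacles are rationale. They promise no second threshold, and the RIC-arm figures the plan collects answer them. How a descriptive primary outcome is tabulated by arm is commonly left to the statistical analysis plan, which is not at hand.

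**Conclusion.** The concern does not hold. A pooled rate within 25% can coexist with RIC non-completion of 5/15 to 7/15 when there are two or fewer crossovers. That follows from combining two arms; it is not an error in the plan. The pooled definition suits the stated aim, no decision or claim rests on 25%, and the RIC-arm rate can be read directly from what the plan defines and records. What remains is a benchmark sentence that could name its denominator. Whether 25% should also be read on 15 RIC patients is a preference, and at that size the reading would be imprecise (exact 95% interval 7.8% to 55.1% at 4/15).

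This conclusion assumes that the analysis stays descriptive, as the Analyses section says, and that attrition is reported by arm, as the within-group precision statement implies. If the pooled 25% were later used alone as a rule for proceeding, the question would have to be reopened.

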Cardiac arrest involves sudden, global ischemia. Quick restoration of blood flow is essential to reduce the chance of death after cardiac arrest. Patients who have restoration of blood flow post cardiac arrest have about a 50% chance of surviving to discharge from hospital. While restoration of blood flow (reperfusion) is necessary to prevent immediate death, it triggers the release of circulating inflammatory molecules including cytokines (e.g. IL-1ra, IL-6, IL-8, IL-10), activated complement and polymorphonuclear leukocytes.⁽⁷⁻¹⁰⁾ These fluxes are associated with upregulation of DNA, endothelial dysfunction, release of reactive oxygen species (ROS) and opening of mitochondrial permeability transition pores (MPTP).^(7, 11-13) The latter plays a critical role in myocardial necrosis.^(14, 15) After cardiac arrest, non-survivors have plasma IL-6 concentrations that are about 20-fold greater than survivors,⁽⁷⁾ which in turn are about 50-fold greater than normal human baseline values.⁽¹⁶⁾ These changes contribute to poor capillary perfusion, tissue ischemia, multi-organ dysfunction and death.⁽¹⁷⁻²⁰⁾ Similar cellular changes are observed after restoration of flow in patients with acute myocardial infarction or coronary artery bypass grafting (CABG). The extent of this reperfusion injury (RI) correlates with the duration of blood flow cessation and impacts how well the patient responds to treatments, as well as the likelihood of death. However, many patients with early hemodynamic dysfunction that is reduced or treated do survive to have a good neurological outcome^(7, 21) and treatments that decrease early mortality related to inflammation and intractable shock could increase the number of survivors with good neurological outcomes.

ATTENUATION OF REPERFUSION INJURY BY INDUCED HYPOTHERMIA

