Individual randomized trial with stratification by rhythm and permuted blocks of concealed size (Figure 2). To reduce potential bias due to using quasi-random methods or envelopes,^(98, 99) we will place sequentially numbered identically appearing active and sham RIC packages, which will be stored ready for use in a central location in the ED. When an eligible patient arrives in the ED, the medical assistant involved in their care will retrieve the next package and open it at the patient's bedside.

SETTING

Patients will be enrolled after transportation to Harborview Medical Center, Seattle, WA which annually receives a high-volume (≥ 50) of patients resuscitated from OHCA, is capable of performing PPCI 24 hours per day, seven days per week, and is staffed by investigators with a special interest in cardiac resuscitation.

[figure not shown]
POPULATION

Included will be those with:

- a) Age 18 years or more;
- b) Defibrillation by laypersons or defibrillation and/or chest compressions by EMS providers dispatched to the scene;
- c) Non-traumatic etiology of arrest, defined as without concomitant blunt, penetrating, or burn-related injury, or uncontrolled bleeding or exsanguination;

- d) Spontaneous circulation upon emergency department arrival;
- e) No response to verbal commands; and
- f) Ongoing or planned induced hypothermia.

FIGURE 2: DESIGN

Excluded will be those with:

- a) STEMI indicated on first 12-lead ECG obtained after restoration of circulation, defined as ST-elevation of ≥ 2 mm in two or more contiguous ECG leads;
- b) Written do not attempt resuscitation (DNAR) reported to providers before randomization;
- c) Drowning or hypothermia as cause of arrest;
- d) Known prisoner or pregnant; or
- e) Dialysis fistula in either upper extremity; or
- f) Pre-existing amputation of upper extremity.

STUDY TREATMENTS

Experimental Device

A standard non-invasive blood pressure cuff (e.g., American Diagnostics Corporation, Hauppauge, NY but any one can be used off the shelf) and disposable plastic clamp (e.g., Medline Industries Incorporated, Mundelein, IL) can be used to apply RIC in patients resuscitated from OHCA via three cycles of 5-mins. inflation to 200 mmHg followed by 5-mins. deflation of a blood pressure cuff on a thigh. The cuff occludes the artery; the clamp maintains pressure in the air bladder of the cuff during the inflation periods.

Control Group

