The effectiveness of other components of post-resuscitation care remains unclear because observational studies may overestimate the effects of treatment vs. randomized designs.^(116, 117) Importantly, we will mandate those components of post-resuscitation care likely to be associated with survival benefit and monitor others. Mandated components will include: emergent coronary angiography in patients with VF; timing of prognosis assessment and withdrawal of care; and implantable defibrillator insertion as indicated. Prohibited will be sedation with propofol. Monitored components will include: hemodynamic monitoring and support; seizure prevention and control; insulin therapy and oxygenation.

Intervention Group

The intervention group will have an RIC package opened at the bedside as soon as feasible after ED arrival. This package will be identical in size, weight and appearance as that in the control group, but will contain a manual blood pressure cuff and a clamp. The medical assistant will place the cuff around the left upper arm in the usual manner midway between the shoulder and elbow, inflate the cuff by pumping air from a bulb held in her hand through a tube into the cuff's bladder, then place a clamp on the tube to prevent air from leaking out of the bladder. The left arm is the preferred limb so as to leave the right thigh and wrists available for emergency coronary angiography. The left thigh is an alternative site but application of RIC to the upper extremity may be superior than application to the lower extremity.⁽⁸³⁾ The cuff will be kept inflated for 5 minutes then deflated for 5 minutes by the medical assistant intermittently inflating the cuff and applying the clamp or reversing the procedure. This will be repeated for three cycles (i.e. 35 minutes total—last 5 minutes is deflation). All other resuscitative measures will be the same as the control group.

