STEMI assessed as the presence of electrocardiographic (ECG) and biomarker criteria for acute myocardial infarction within 48 h of the index arrest.⁽¹²⁸⁾ Note that ST-elevation on the first 12-lead ECG after resuscitation is a poor predictor of acute infarction in this population.⁽¹²⁹⁾ These patients often develop infarctions during the subsequent 48 h.

Myocardial Injury assessed as peak serum troponin in ng/mL at any time point within 24 h of index arrest.

Renal Dysfunction assessed using Risk, Injury, Failure, Loss, End Stage criteria.^(130, 131)

Hospital Free Survival (HFS) assessed as number of days alive and permanently out of hospital up to 30 days post arrest. Patients who die before discharge will be assigned zero days out of hospital. Note that other randomized trials that enrolled patients with cardiac arrest have described similar outcomes such as days on a ventilator, in an intensive care unit or in hospital.^(31, 132, 133) However such assessments were potentially limited because they did not account for the differential timing of mortality. Importantly, HFS has been used as an outcome in trials in patients with heart failure,^(134, 135) renal failure,⁽¹³⁶⁾ cancer,⁽¹³⁷⁾ or need for intensive care.⁽¹³⁸⁾ As well, HFS is recommended as an outcome in trials that enroll patients with need for intensive care.⁽¹³⁹⁾ The description of HFS will provide additional granularity to our results.

Withdrawal of Care assessed as the reduction of support (i.e. reducing pressors, lab draws or medications) or withdrawal of support (i.e. extubation, stopping drips/meds, changing to comfort care only) during hospitalization.

Favourable Neurologic Status at Discharge assessed using modified Rankin Score (MRS) ≤ 3 at hospital discharge or 30 days after index arrest.

Survival to Discharge assessed as alive when discharged from hospital to home, nursing facility or rehabilitation. Patients transferred to another acute care facility (e.g. to undergo implantable defibrillator placement) will be considered still hospitalized.

Clinical Instability at Discharge assessed using the Kosecoff Index⁽¹⁴⁰⁾ measured at discharge based on the presence of nine symptoms and signs associated with increased risk of rehospitalization. Instability will be the presence of any of these.

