Survival to 30 Days After Cardiac Arrest assessed as alive 30 days after the index cardiac arrest as confirmed by a brief telephone interview. Note that some experts suggested that the primary outcome of trials in patients with OHCA should be assessed 90 days after discharge.⁽¹⁴¹⁾ However, we showed that such post-discharge scores were well correlated with assessments before discharge.⁽¹⁴²⁾ As well, post-discharge assessment was susceptible to informative missingness as the characteristics of those who consented for follow up were different from those who did not. Lyden and colleagues made similar observations about short vs. long-term outcomes after stroke.⁽¹⁴³⁾ Importantly, post discharge assessments burden patients and prolong study duration. We will confine post-discharge assessment to a brief telephone interview at 30 days.

Accrual is the proportion of eligible subjects who have the study device applied.

SAFETY OUTCOMES

Expected Adverse Events

Device Failure Malfunctions are unlikely due to the simple construction and durable materials of the devices. However, device failure will be defined as discontinuation of use of the device prior to the end of allocated treatment interval because of mechanical failure as opposed to provider preference.

Related to Device RIC is generally well-tolerated, but several side effects will be monitored. Most important are pain at the site of application, or thrombophlebitis, or infection.

Pain assessed using the Richmond Agitation-Sedation Scale at 30 and 60 minutes after randomization in control and intervention group patients.^(144, 145) No gold standard exists for pain assessment in sedated and ventilated patients.⁽¹⁴⁶⁾

Thrombophlebitis assessed as symptomatic non central nervous system venous or arterial thrombus documented radiographically or ultrasonographically.

Sepsis assessed within one week of index arrest as either i) the presence of microbiologically proven, clinically proven, or suspected infection; or ii) presence of Systemic Inflammatory Response Syndrome (SIRS); and iii) development of at least one organ dysfunction within the preceding 24 hours.⁽¹⁴⁷⁾

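### The Withdrawal of Care outcome is defined by acts without regard to reason, so as written it counts patients weaned or extubated because they recovered together with patients moved to comfort care

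*Protocol*

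**What the plan says.** Under Secondary and Exploratory Outcomes, the protocol gives the definition in two limbs. Withdrawal of Care is "assessed as the reduction of support (i.e. reducing pressors, lab draws or medications) or withdrawal of support (i.e. extubation, stopping drips/meds". The second limb reads in full "or withdrawal of support (i.e. extubation, stopping drips/meds, changing to comfort care only) during hospitalization". The limbs are joined by *or*, each list is introduced by *i.e.*, and the window is the whole hospital stay.

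The only other mention of the concept is under Study Treatments, where the mandated parts of post-resuscitation care include "timing of prognosis assessment and withdrawal of care". That passage fixes no criterion for the outcome.

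Two other definitions in the protocol do carry a condition on cause or reason. Cardiogenic shock is a low pressure "within 48 h of the index arrest not due to a correctable cause". Device failure is discontinuation "because of mechanical failure as opposed to provider preference".

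**The concern.** Each listed act can mark either of two opposite courses. Pressors are reduced, blood draws become less frequent, infusions are stopped and the tube is removed when a patient gets better. The same things happen when treatment is limited because the outlook is poor. Only the comfort-care item belongs to one course alone, and it is one alternative among several.

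The trial enrols patients who meet the criterion "No response to verbal commands; and" who have ongoing or planned induced hypothermia. A survivor from this group who was intubated, or on pressors or infusions, would ordinarily pass through at least one listed step before discharge.

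At stake is what the descriptive count means. If recovery and limitation of life support are pooled, the count cannot be read as the frequency of the event it names, and a difference between arms has no clear direction. The study is meant to inform the design of a later trial, so the definition could be carried forward.

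**Working it through.** The protocol gives no figure for this outcome, so there is none to reproduce. The check is first textual, then a rough sizing.

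**Text.**
- *I.e.* makes the listed acts the definition and not a set of examples.
- *Or* makes either limb sufficient.
- No reason, intent or prognosis is required in the definition, and nothing elsewhere in the protocol adds one.
- The cardiogenic shock and device failure definitions show that the protocol writes such a condition elsewhere. None is written here.

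**Inputs for the sizing.**
- N = 30, 15 per group (Sample Size).
- S, survival to discharge: about 0.50. The Reperfusion Injury section says: "Patients who have restoration of blood flow post cardiac arrest have about a 50% chance of surviving to discharge from hospital". Human Subject Issues gives a matching mortality of about 50% before discharge.
- S, alternative: the Burden section gives about 55% of treated patients with a perfusing rhythm on transport, and 10% of those treated surviving. If both percentages have all treated patients as denominator, S = 10/55 = 0.18.
- e, share of survivors weaned or extubated: 0.8 to 1.0 (assumption, not in the protocol).
- w, share of in-hospital deaths that follow a true decision to withdraw: 0.25 to 0.75 (assumption, not in the protocol).

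**Formulas.**
- Counted because of recovery: N × S × e
- Intended count: N × (1 − S) × w
- Count as written: the sum of the two

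**Results.**

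| | S = 0.50 | S = 10/55 |
|---|---|---|
| Survivors of 30 | 15 | 5.5 |
| Counted for recovering, e = 0.8 to 1.0 | 12 to 15 | 4.4 to 5.5 |
| Deaths of 30 | 15 | 24.5 |
| Intended count, w = 0.25 to 0.75 | 3.75 to 11.25 | 6.1 to 18.4 |
| Count as written, e = 1.0 | 18.75 to 26.25 | 11.6 to 23.9 |
| Recoveries as share of that count, e = 1.0 | 57% to 80% | 23% to 47% |

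The number counted for recovering does not depend on w.

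**Direction.** As a rate, the count as written is S·e + (1 − S)·w = w + S·(e − w). Over the ranges above e exceeds w, so this rate rises with survival, while the intended rate (1 − S)·w falls. An arm with more recoveries could therefore show more withdrawal of care while having fewer true withdrawals. The formula leaves out patients who die without a withdrawal decision but have some medication reduced. They too would meet the wording, and counting them would weaken this contrast.

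**The case against.** The strongest reply is that the intent is plain. The outcome's name, the comfort-care item, and the pairing of withdrawal with prognosis assessment under Study Treatments all point to limitation of life support. A sensible abstractor is unlikely to enter a patient who was extubated and went home. Hemodynamic support is also listed separately as a monitored component of care. This stands as evidence of what was meant, but it does not restrict the other listed acts. An abstractor must either follow the text and pool the two courses, or apply an unwritten rule that another abstractor may not share.

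Second, survival to discharge and the modified Rankin score are recorded for the same patients, so a cross-tabulation would separate many weaned survivors from patients who died after withdrawal. That is a partial remedy. It does not sort patients who were extubated and died later, or deaths in which some support was reduced without any decision to limit care. For that reason it would be too strong to call the outcome uninformative.

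Third, this is one of many secondary or exploratory outcomes in a 30-patient pilot, and the Analyses section plans descriptive summaries without comparison and no claims. That stands and limits the weight of the point.

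A reader might also infer that an ordinary early pressor wean would be reported as early withdrawal in the periodic care-process summaries. The protocol does not support this: Monitoring of Concurrent Care does not apply the outcome definition to those summaries, and says they are given without patient outcomes. Nor does the protocol say why it records this outcome, or that it is the only source on withdrawal decisions. The timing of withdrawal is separately mandated as a part of care.

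**Conclusion.** The point holds as a defect in a definition that the protocol itself states. Read as written, Withdrawal of Care pools recovery with limitation of life support. The number counted for recovering is about 12 to 15 of 30 at 50% survival and about 4 to 5 of 30 at 18%, in both cases assuming that 80 to 100% of survivors are weaned or extubated.

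Two stronger statements are tempting. One is that the outcome would be met by nearly everyone. At 50% survival, with every survivor counted, the total is about 19 to 26 of 30, which is high but not universal. The other is that most of those counted would be recoveries. In the table that holds at 50% survival and fails at 18%, where recoveries are about 23% to 47% of the count. The Burden figures permit the lower reading, and both survival figures describe resuscitated or treated patients generally, not the enrolled subset. Neither statement should be made.

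The primary attrition outcome, the sample size and patient care are unaffected.

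**What to change.** Define the outcome as a documented decision to limit, reduce or withdraw life-sustaining treatment, or to change to comfort care, made because of expected poor outcome or the wishes of the patient or family. Record its date, time and reason. State that reductions in pressors, medications or lab draws, and extubation, do not count when they are due to clinical improvement.

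This rewords one definition and needs one reason field with date and time, filled from the daily record review already planned under Monitoring for Outcomes. It changes what is measured and no clinical rule. The downside is slightly more abstraction and some judgement about documented intent.
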